8.3.2. Inhibitor Development

Inhibitor results of the Nijmegen-modified Bethesda Assay from the central lab will be listed. Results from blood samples collected during surgical/rehabilitation periods for the purpose of determining the presence of an inhibitor will be included.

A positive inhibitor occurs where a subject has a value ≥ 0.6 Bethesda Units (BU/mL) confirmed on re-testing between 2 and 4 weeks later. Both tests must be performed by the central laboratory.

A “low” titer inhibitor occurs where a subject has a value between 0.6 and <5.0 Bethesda Units (BU/mL) confirmed on re-testing between 2 and 4 weeks later.

A “high” titer inhibitor occurs where a subject has a value ≥ 5.0 Bethesda Units (BU/mL) confirmed on re-testing within 2 to 4 weeks.

8.3.3 Incidence of Anti-rFVIII Fc Antibodies

The development of anti-rFVIII Fc antibodies will be assessed as the number and percentage of subjects negative throughout the study, positive at any time following study 8HA01EXT Study Day 1, and positive at the final evaluation. Percentages will be based on the number of subjects who are antibody negative prior to study 8HA01EXT baseline and have at a post baseline antibody evaluation for the referenced time point or time interval.

Results from blood samples collected during surgical/rehabilitation periods for the purpose of determining the presence of anti-rFVIII Fc antibodies will be included in this analysis.

In addition to a listing of all anti-rFVIII Fc antibody results, a separate listing of all results from subjects with at least one positive outcome during the study, including at baseline, will be provided.

8.4. Vital Signs

Vital signs (systolic and diastolic blood pressure, pulse, respiratory rate, and oral temperature) will be summarized for the observed values and change from baseline using descriptive statistics for the Safety Analysis Set.

The number and percentage of subjects with clinically relevant post-baseline abnormalities will be presented. The criteria for clinically relevant post-baseline abnormalities are shown below in Table 4.

Table 4 Criteria to Determine Clinically Relevant Abnormalities in Vital Signs

Vital Sign	Criteria for Abnormalities
Temperature	>38°C and an increase from pre-dosing of at least 1°C
Pulse	>120 beats per minute post-baseline, or an increase from pre-dosing of more than 20 beats per minute, or <50 beats per minute post-baseline, or a decrease from pre-dosing of more than 20 beats per minute
Systolic Blood Pressure	>180 mmHg post-baseline, or an increase from pre-dosing of more than 40 mmHg, or <90 mmHg post-baseline, or a decrease from pre-dosing of more than 30 mmHg
Diastolic Blood Pressure	>105 mmHg post-baseline, or an increase from pre-dosing of more than 30 mmHg, or <50 mmHg post-baseline, or a decrease from pre-dosing of more than 20 mmHg

A listing of all vital signs (added height and weight) will be provided, including from unscheduled visits and during surgical/rehabilitation periods. Vital signs collected during surgical/rehabilitation periods as well as those occurring on the day of surgery will be flagged in this listing.

9. Sensitivity Impact Assessment

As proposed under the MHRA CAPA commitment, an analysis will be performed to assess the impact of the EPD query process and addition of manually created records on the results of study 8HA01EXT. The analysis will include summary tables that will be re-run plus any additional summary tables or listings required for inclusion in the final clinical study report (CSR).

Background

Subject recorded diary data was queried via a defined process which originally required confirmation with the subject of **all** changes. Subsequently, it was identified that this did not occur in all cases nor was this actually necessary for all types of change. In 2014, it was agreed that only certain categories of changes required subject confirmation, and a process implemented to ensure adequate documentation to support those changes was available. After a subsequent MHRA audit in 2015, further consideration was given to the timing of changes relative to the actual data generation, reliable subject recall period, and still lack of appropriate documentation to support changes in all cases. Therefore, taking into consideration these findings and industry standards to limit changes of subject reported data, the query process was updated to **only allow changes defined as not requiring subject confirmation**. Although changes classified as SVC/L60 did not require subject confirmation (as agreed with MHRA in 2014), these changes will no longer be made directly into the data, but will be applied via a programmatic data convention (details described in Section 5.4).

The Total Query Report (TQR) documents all changes to the EPD data. The changes in this report were classified according to a pre-defined list (see table below).

Code	Description	Requires subject confirmation
LN	Minor lot # change (addition/deletion of spaces or hyphens) and Major lot # change (any other changes to lot #)	N
D/EPD	Duplicate entry in EPD by subject - deleted	Y
D/CRF	Entry in EPROLOG is also in CRF/INFORM as in-clinic dose	N
Dose	Vials added or removed	Y
SVC	Single vials combined - entered as separate injections in error	Y
SVC/L60	Single vials combined - entered as separate injections in error – injection time range for combined records is ≤ 60 mins	To be applied via programmatic data convention during analysis as described in Section 5.4
Error	Subject entered in error - entry deleted	Y
DTOI	Date and/or time of injection corrected	Y
Pre-Fc	Entries deleted as prior to first dose with Fc (not required per protocol)	N
Train	Entries deleted as training/prior to first dose with Fc (not required per protocol)	N
Test subject	Subject does not exist - entries deleted	N

Code	Description	Requires subject confirmation
Inj Reason	Reason of injection changed (other than routine prophylaxis or other to surgical prophylaxis if a confirmed minor/major surgery or procedure is capture in the eCRF during the defined surgical period or date of procedure; or from new bleed to follow up)	Y
Inj Reason Surgery	Injection reason from routine prophylaxis or other to surgical prophylaxis	N
BLD LOC	Change in Bleed Location	Y
BLD TYP	Change in Bleed Type	Y
BLD SYM	Change in Bleed Symptoms	Y
DTOB	Date and/or time of bleed corrected	Y
Activity	Change in Physical Activity question	Y
TRT SD	Amendment to Treat with Study Drug item: “Did you inject with rFVIIIFc (Study Drug)?”	Y
TRT BLD	Amendment to Treat Bleed item: “How did the bleed respond to injection on ...”	Y
Abandon	Query request was raised but then cancelled by site	N
In-clinic administration	In-clinic administration entered in EPD and corrected in reference to source records	N
NBTFU	Injection to treat the bleed is < 72 h of the previous injection to treat the existing bleed New bleed deleted, follow up inj to existing bleed added (per protocol definition)	N
Tx Arm/Reg	Change in treatment arm or regimen	N
ADMIN	Changes made by site to data fields that the site would have entered originally and/or are administrative. E.g. study name or data entered into an incorrect field and corrected, data entered that is not required, expiry date of IMP extended, data field changes that are duplicated due to multiple site staff involved in the query process or similar, correction of injection reason related to treatment arm, e.g. routine prophylaxis to weekly dose for subjects on a weekly regimen	N

In certain circumstances, where subjects could not enter records directly into the EPD for any reason, records were requested to be created manually by the site according to a pre-defined documented process which included SDV by CRA. However, it was subsequently identified that confirmation of SDV could not be provided. Records were re-SDVed at site to determine whether source was available, or whether contemporaneous documentation of confirmation with the subject was available. *(Not discussed further in this SAP).*

For the impact assessment, all data record changes requiring subject confirmation will be set back to the original values. Although changes classified as SVC/L60 did not require subject confirmation (as agreed with MHRA in 2014), these changes will no longer be made directly into

the data, but will be applied via a programmatic data convention (described in Section 5.4). Manually created data without complete SDV of the record versus a paper diary will be considered unsupported by SDV at site, and will be removed for the purpose of the impact assessment. SDTM and ADAM datasets will be re-created and certain statistical analyses re-run. Endpoints covered under the impact assessment include:

- exposure
- annualized number of bleeding episodes per subject (ABR)
- subjects assessment of response to treatment with rFVIII Fc for bleeding episodes
- number of injections and dose per injection of rFVIII Fc required to resolve a bleeding episode
- prophylactic dose and dosing interval

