1. End of Treatment (EOT) visit for the preceding study may serve as the Screening Visit for the extension study. Written informed consent and subject assent, if applicable, for participation in the extension study must be obtained at this visit before any extension study-related procedures are conducted. Parents/legal guardians should receive the informed consent information prior to this visit to allow adequate time for review at home, and discussion with the Investigator and/or designee. Data on medical history, demographics, screening tests, ongoing adverse events (AEs) and concomitant therapy, and EOT tests and assessments will be transferred from the preceding rFVIIIIFc studies. Thus, it will not be necessary to repeat these assessments at Visit 1. An HJHS or modified HJHS assessment, as appropriate, should be performed at Visit 1 in ALL subjects. Study eligibility must be verified prior to study enrollment. Subjects who enroll with a gap of greater than 37 days following EOT Visit of the previous study should have all laboratory assessments performed and reviewed by the Investigator at Visit 1, prior to dosing with rFVIIIIFc, to assess safety and inclusion/exclusion parameters. The time required for Visit 1 may span a sufficient interval to allow for laboratory results to be reviewed and confirmed as suitable by the Investigator, and may require more than 1 clinic visit prior to dosing with rFVIIIIFc.
2. For future subjects that enroll into ASPIRE, assessments will be only those conducted in the parent study.
3. Medical and surgical history includes any significant medical condition and/or any significant surgical histories that have occurred since the subject enrolled in the parent study.
4. Physical examination and vital signs. Physical examination to include: skin, head, eyes, ears, nose, throat (HEENT); lymph; neck; chest/lungs; heart; vascular; abdomen; musculoskeletal; neurological; extremities; and joints. Vital signs to include: temperature, blood pressure, pulse rate, and respiratory rate. Following Visit 7, physical examination and vital signs continue to be performed only annually.
5. Subjects will receive supplies of rFVIIIIFc for home administration from the study site at and between visits; each time, the study site staff will perform full medication exchange and accountability with the subject, or the subject's caregiver. See Section 12 for information on planning and process for dispensation, and on supplies accountability.

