5.1. General Principles

The following rules will be followed for all applicable analyses contained in this SAP, unless specified otherwise.

Because the subjects from studies 997HA301/997HA307/997HA309 and study 8HA02PED are in different age groups (i.e. ≥ 12 years of age for studies 997HA301/997HA307/997HA309 and < 12 years of age for study 8HA02PED) and may therefore have different safety and efficacy profiles, analyses will be performed separately for the groups of subjects from the parent study or parent studies combined, as described in the table below. Further, the table categories (i.e. age cohort, treatment regimen, etc) by type of analyses for each grouping are also detailed unless specified otherwise.

Groups of subjects from the parent study or parent studies combined	Categories by type of analyses
8HA02PED	Baseline/Concomitant therapy and procedures: Age cohort and overall; treatment regimen (including surgery subgroup) and overall Exposure: Age cohort and overall; treatment regimen and overall Efficacy: Age cohort; treatment regimen Patient-reported outcomes: Age cohort and overall; visit Compliance/surgery/Safety: Visit (if applicable)
997HA301 997HA301/997HA307/997HA309 combined	Baseline/Concomitant therapy and procedures: Treatment regimen (including surgery subgroup) and overall Exposure: Treatment regimen and overall Efficacy: Treatment regimen

	Patient-reported outcomes: Visit Compliance/surgery subgroup/Safety: Visit (if applicable)
Overall	Compliance/Surgery/Safety: Visit (if applicable)

Where treatment regimen (which is defined as treatment regimen in study 8HA01EXT) is:

- Tailored prophylaxis
- Weekly prophylaxis
- Personalized prophylaxis
- Episodic

Age cohort for subjects from study 8HA02PED is as reported for that study, namely:

- <6 years old
- 6 to <12 years old

Summaries of study 8HA01EXT data will be produced using standard summary statistics. Listings will also only include data from study 8HA01EXT and the treatment regimen associated with each data point, unless specified otherwise. Data collected at unscheduled visits will be included in the definition of the maximum and minimum post-baseline values.

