8.3.1.3 Potentially Clinically Significant Laboratory Abnormalities

Abnormal laboratory values will also be evaluated by determining the number and percentage of subjects with at least one potentially clinically significant laboratory abnormality over the course of the study that also represents a worsening from baseline. The potentially clinically significant levels are based on Grade 2 or higher thresholds from the Common Toxicity Criteria for Adverse Events (CTCAE v 4.02 2009) where possible, or were defined by Bioverativ's Safety and Benefit Risk Management group. Subjects who have a post baseline laboratory value that meets the criteria for being potentially clinically significant but do not have a baseline value will be included in the numerator for determining the percentage of subjects with an abnormality. Percentages will be based on the number of subjects with at least one post baseline value for the given laboratory test. Threshold levels for potentially clinically significant laboratory abnormalities are provided in [Table 2](#) (hematology) and [Table 3](#) (chemistry). Data collected from unscheduled visits will be included in this analysis.

Table 2: Threshold Levels for Potentially Clinically Significant Hematology Abnormalities

Subjects from studies 997HA301/997HA307/997HA309		
	Low	High
White blood cells	$<3.0 \times 10^9/L$	$\geq 16 \times 10^9/L$
Lymphocytes	$<0.8 \times 10^9/L$	$>12 \times 10^9/L$
Neutrophils	$<1.5 \times 10^9/L$	$>13.5 \times 10^9/L$
Monocytes	NA	$>2.5 \times 10^9/L$
Eosinophils	NA	$>1.6 \times 10^9/L$
Basophils	NA	$>1.6 \times 10^9/L$
Hemoglobin	$\leq 115 \text{ g/L}$	$\geq 190 \text{ g/L}$
Hematocrit	$\leq 37\%$	$\geq 60\%$
Platelet count	$\leq 75 \times 10^9/L$	$\geq 700 \times 10^9/L$
Subjects from study 8HA02PED		
	Low	High
Neutrophils	$<1.5 \times 10^9/L$	NA
Eosinophils	NA	$>1.6 \times 10^9/L$
Hemoglobin	$<100 \text{ g/L}$	Increase in $>20 \text{ g/L}$ above ULN
Hematocrit	$<30\%$	$\geq 60\%$
Platelet count	$\leq 75 \times 10^9/L$	$\geq 700 \times 10^9/L$

NA = not applicable

Table 3: Threshold Levels for Potentially Clinically Significant Chemistry Abnormalities

Subjects from studies 997HA301/997HA307/997HA309		
	Low	High
Liver		
ALT/SGPT	NA	$\geq 3 \times \text{ULN}$
AST/SGOT	NA	$\geq 3 \times \text{ULN}$
Total bilirubin	NA	$\geq 34.2 \mu\text{mol/L}$
Renal		
Blood urea nitrogen	NA	$\geq 10.7 \text{ mmol/L}$
Creatinine	NA	$\geq 176.8 \mu\text{mol/L}$
Electrolytes		

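### SAP Table 4 applies one set of vital-sign limits to all ages and measures change from an undefined reference, so the pediatric abnormality counts will be hard to interpret

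*SAP*

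**What the plan says.** SAP 8.4 commits to a count: "The number and percentage of subjects with clinically relevant post-baseline abnormalities will be presented". The criteria in Table 4 carry no split by age or parent study:

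- Pulse: ">120 beats per minute post-baseline, or an increase from pre-dosing of more than 20 beats per minute", with mirror-image rules for values below 50 and falls of more than 20.
- Systolic: ">180 mmHg post-baseline, or an increase from pre-dosing of more than 40 mmHg, or <90 mmHg post-baseline", or a fall of more than 30 mmHg.
- Diastolic: ">105 mmHg post-baseline, or an increase from pre-dosing of more than 30 mmHg, or <50 mmHg post-baseline", or a fall of more than 20 mmHg.
- Temperature: ">38°C and an increase from pre-dosing of at least 1°C".

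The population is the Safety Analysis Set: everyone dosed in 8HA01EXT, whichever parent study they came from (SAP 4.3).

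Elsewhere the SAP treats age as a reason to separate subjects. SAP 5.1 says the groups "may therefore have different safety and efficacy profiles". In SAP 8.3.1.3, Tables 2 and 3 each contain a block headed "Subjects from study 8HA02PED" with its own limits. For example, the low hemoglobin threshold is <100 g/L for children and ≤115 g/L for the older group, and high creatinine is >1.5 × ULN for children and ≥176.8 µmol/L for the older group.

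On the reference value, SAP 5.1 sets the default baseline as the last usable measurement on or before 8HA01EXT Study Day 1. The text of SAP 8.4 summarizes change from baseline, and the list of tables titles the abnormality output by reference to the 8HA01EXT baseline. Only the cells of Table 4 refer to pre-dosing.

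**The concern.** There are two separate problems.

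First, a fixed cut-off is a fair marker of abnormality only if subjects' usual values lie at a similar distance from it. A child whose ordinary systolic pressure is not far above 90 will cross that floor through normal visit-to-visit variation; an older subject with a higher usual value will not. Both are counted under the same label. The SAP accepted this reasoning for laboratory tests and gives no reason for dropping it one section later.

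Second, pre-dosing has at least three readings: before the first rFVIIIFc dose in the parent study, before a dose given at a clinic visit, or the 8HA01EXT baseline. The distinction is real because, for prophylaxis subjects with a short gap or none, Study Day 1 is generally the day of the last parent-study dose (SAP 5.1.1). Two programmers could follow Table 4 and produce different change counts.

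At stake is whether one descriptive safety table can be read for the children, and how far their column moves the overall total. The study's primary objective is long-term safety, so the pediatric column should mean something.

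**Working it through.** **Plan's own figures.** The documents state no expected rate of vital-sign abnormalities, so there is no such figure to reproduce. The denominator can be checked: 144 + 50 + 12 + 8 = 214, matching SAP 3.1 and 3.3.1. The planned 8HA02PED subjects are 50/214 = 23.4%. The cohort under 6 is 25/214 = 11.7% (Protocol 5.1.3). That is age in the parent study, so 25 is a ceiling for subjects still under 6 during the extension.

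**Number of readings.** Visits are 6-monthly, and "Following Visit 7, physical examination and vital signs continue to be performed only annually" (Protocol, footnote 4 to the Screening and Treatment Period schedule). If vital signs are taken at Visits 2 to 7 and then once more by year 4, there are 6 + 1 = 7 post-baseline sets. This is an assumption, because the schedule grid is not in the available text.

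**Model (assumed; the documents give no values).** Reading = mean *m* + between-subject normal deviation (SD *b*) + within-subject normal deviation (SD *w*), with one baseline and 7 later readings.

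Single visit: P(systolic < 90) = Φ((90 − m)/√(b² + w²)).
- m = 95: Φ(−5/√61) = 26% for SDs 6/5; Φ(−5/√128) = 33% for SDs 8/8.
- m = 120: Φ(−30/√61) ≈ 0%; Φ(−30/√128) = 0.4%.

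Ever outside limits L and U over 7 visits: 1 − ∫[Φ((U − m − bz)/w) − Φ((L − m − bz)/w)]⁷ φ(z) dz. For m = 95 this gives 60.1% and 73.0%. A simulation of 200,000 subjects per scenario, with the change rules added, gives 60.1% and 73.2%.

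| Systolic mean | One visit, absolute limits | Ever flagged, no growth | Ever flagged, +3 mmHg/year |
|---|---|---|---|
| 95 | 26-33% | 60-73% | 33-53% |
| 100 | 10-19% | 31-54% | 13-33% |
| 105 | 3-9% | 11-34% | 3-18% |
| 110 | 0.5-4% | 3-18% | 0.5-8% |
| 120 | 0-0.4% | 0-4% | 0-2.5% |

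Each range runs from SDs 6/5 to 8/8.

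*Diastolic* (SDs 5/5 to 7/7, no growth), ever flagged: mean 55, 62-72%; mean 60, 29-51%; mean 75, 1.5-14%.

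*Pulse, absolute limits* (SDs 8/6 to 10/10, no growth), ever outside 50-120: mean 105, 22-45%; mean 95, 3-17%; mean 85, 0.3-7%. At mean 70 it is 9-29%, through the lower limit.

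*Pulse, change rule* (more than 20 either way, no growth): about 10% for w = 6 and 57% for w = 10, whatever the mean. A fall of 4 beats per minute per year raises these to about 44% and 72%.

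**Effect on the overall total (upper bound).** If all 25 planned children under 6 had mean systolic 95 throughout, 25 × 0.601 = 15.0 to 25 × 0.732 = 18.3 would be flagged. That is 7.0% to 8.6% of 214. With growth of 3 mmHg/year, 25 × 0.332 = 8.3 to 25 × 0.529 = 13.2, or 3.9% to 6.2%. At mean 120 the same 25 would contribute about 0 to 1.1 subjects.

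**Growth and the rise criteria.** To reach a rise of more than 40 systolic or 30 diastolic through growth alone over 4 years, pressure would have to increase by more than 40/4 = 10 or 30/4 = 7.5 mmHg per year.

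**The case against.** The case for leaving the table alone has some force.

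- SAP 8 displays safety by parent-study group as well as overall, so the older subjects' column is not contaminated. This stands. It separates the columns but leaves the criteria unchanged, so the pediatric column and the overall total keep the problem.
- Observed values, changes from baseline and a full listing are also planned, and adverse events are collected independently. This stands, and it is why the point is small. A reader might infer that a real safety signal would be hidden; given these other outputs, the documents do not support that.
- SAP 5.1 and the table title already point to the 8HA01EXT baseline. This largely stands. The defect is inconsistent wording. A reader might go further and infer that no pre-dose reading is ever taken. That cannot be shown: the schedule grid is missing from the available text, and parent-study end-of-treatment assessments are carried over.

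A reader might also infer that the pediatric counts will mostly reflect age and growth. The documents give no pediatric pulse or blood-pressure values, so this holds under some assumptions and fails under others. Rising blood pressure reduces low-pressure flags, as the table above shows, and is unlikely by itself to meet the rise criteria. If within-subject pulse SD is 10, most pulse-change flags come from ordinary variation at any age. Only the pulse-fall rule clearly supports a growth effect.

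Finally, Table 4 is not labelled as an adult table. What can be said is that it makes no provision for age.

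**Conclusion.** The point holds as an internal inconsistency in the SAP. Table 4 uses one set of absolute limits for all ages, while SAP 5.1 and Tables 2 and 3 treat 8HA02PED separately. Its change criteria use a reference the SAP does not define.

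The dependence of the counts on usual level is strong: 0-4% to 60-73% ever flagged on systolic pressure across assumed means of 120 to 95. Where the study's children fall in that range is unknown. The figures rest on assumed means, normal variation, the stated SDs and 7 readings, and none of the distributional inputs comes from the documents.

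The consequence is limited to a descriptive safety table. No hypothesis is tested, and the primary endpoint, inhibitor development, is not touched. This is a low-cost improvement, not a flaw that threatens the study's conclusions.

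**What to change.** Amend SAP 8.4 as follows.

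1. Keep the present limits for subjects from 997HA301/997HA307/997HA309. Add an 8HA02PED block with criteria by age at the visit, chosen and documented by the sponsor's safety group, as for the laboratory thresholds. Include a band for children who reach 12 during the study, which SAP 3.2 foresees.
2. Replace pre-dosing in every cell with the 8HA01EXT baseline of SAP 5.1, for all subjects. Comparing children with their previous visit instead would remove growth, but it would miss slow cumulative change, which a long-term safety study should see, and would put two comparators in the overall column.
3. Show absolute-limit flags and change-from-baseline flags on separate lines, by age cohort for 8HA02PED.

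The cost is one extra block in one table and minor programming, with no new data. The downside is that the sponsor must choose and justify the pediatric limits. The overall column would also combine two sets of criteria, as it already does for laboratory values.
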